1.2. Study Design

The study is a prospective, single arm, multicenter efficacy study, consisting of 60 subjects who will complete the study (note: if any patients are lost to follow-up or withdrawn, enrollment will increase to compensate for loss of these subjects). The subjects will receive up to 16 RD1 applications. In case of complete healing, subject will be called for one confirmatory visit two weeks later or before discharge from the SNF (the earlier of the two). Subject data will be kept in each site's records.

All diabetic subjects' glycemic management will be performed by a qualified physician. All subjects will have wound care specialist or wound surgeon or dermatologist involved in their wound care

1.3. Subject Population

Up to 120 (or more) subjects will be enrolled at 2 SNF in the US in 2 phases: Phase I- 40 subjects and phase II- 80 subjects). Subjects will be older than 18 years with wounds deemed suitable for treatment with RD1.

1.3.1. Patient that require Legally Authorized Representative (LAR)

The patient population that will be enrolled to the study includes patients that require LAR signature. The rational for inclusion of this population is that the RD1 is an FDA cleared product, that demonstrated significant chronic ulcers healing rates, much superior to known standard of care. In the nursing home, many of patients with chronic ulcers are those that require LAR. By not including those patients in the RD1 study, we are depriving them from

superior treatment and with the prospect of healing their ulcers and we are discriminating them from those patients that do not require LAR. The RD1 was determined by FDA to be a safe product and will be used in the study according to the FDA cleared intended use only.

Enrollment process of patients that require LAR will be according to the local regulations and enrollment procedure per site will be submitted to the IRB in advance including specific requirements in the ICF and the consenting process.

1.4. Study Duration

The study is expected to last 12 to 24 months.

The study per each subject will continue for up to 16 weeks of RD1 treatment (not including up to 2-week screening period (\pm 2 days)), Any wounds that are considered initially healed within the 16-week period will require a confirmatory visit two weeks after healing of before discharge from the SNF (the earlier of the two) to assess durability of wound closure.

Patients will be treated with RD1 every 7 days (\pm 3 days), investigator can prolong the duration between treatments based on medical decision. Total treatment duration is up to 16 weeks or until complete healing.

1.5. Treatment Regimen

Ethics/Institutional Review Board (IRB/EC) committee approved consent is obtained prior to subject participation. The patients will be screened to determine if they meet the inclusion and exclusion criteria. The screening period lasts for up to 14 days \pm 2 days. The target ulcer will be treated with RD1. The RD1 clot is created from the subject's blood in accordance with the procedure described in the RD1 Application Protocol (Appendix 2) and according to accepted precautions guidelines. Patients will be treated with RD1 every 7 days (\pm 3 days), investigator can prolong the duration between treatments based on medical decision. Total treatment duration is up to 16 weeks or until complete healing. The RD1 should be anchored using steri-strips then covered with a primary non-adherent dressing such as Mepitel and then covered using a secondary dressing based on type of wound and amount of exudate.

1.6. Assessment

1.6.1 Screening Phase:

1.6.1.1 Written informed consent.

Informed consent will be obtained by the principal investigator or his or her designee prior to any study-related procedures. When the subject or his/ her legal authorized representative is agreeable to participation in the clinical trial, he/she must understand, sign and date the IRB/EC-approved Informed Consent Document (see sample in Appendix 1), which describes the study and potential

discomforts, risks, and benefits of participating. One copy of the consent form will be provided to the subject and one copy will be maintained with the subject's medical record.

- 1.6.1.2** Execution of inclusion and exclusion criteria.
- 1.6.1.3** Complete medical history and physical examination.
- 1.6.1.4** Collection of patient demographics.
- 1.6.1.5** Complete ulcer history.
- 1.6.1.6** Wound photography before cleansing/ debridement. See Appendices 3-4.
- 1.6.1.7** Wound cleansing
- 1.6.1.8** Wound debridement, if required (Debridement procedures are described in Appendix 9).
- 1.6.1.9** Wound measurement via digital photography. See Appendices 3-5.
- 1.6.1.10** Wound depth measurement by accepted method. Unit of measurement is millimeters
- 1.6.1.11** Wound photography after cleansing/ debridement. See Appendices 3-4.
- 1.6.1.12** Classification and grading of study wound (if applicable).
- 1.6.1.13** Neuropathic assessment (for foot ulcers only).
- 1.6.1.14** Review of ulcer and blood related medications taken by the subject including herbal medications.
- 1.6.1.15** Pregnancy test (urine) for female subjects of child-bearing potential.
- 1.6.1.16** Assessment for infection of the target ulceration.
- 1.6.1.17** Assessment of moisture control, when relevant.
- 1.6.1.18** Assessment of offloading, when relevant.
- 1.6.1.19** Vascular perfusion assessments will be conducted to assess adequate perfusion of the lower extremities using Ankle-Brachial Index (ABI), when relevant. ABI will be determined on the affected side (i.e., the side of the body on which the study ulcer resides) according to standard procedure/protocol at the study site.
- 1.6.1.20** Laboratory. Patients who have had labs drawn within 30 days prior to screening do not require a repeat draw. Otherwise complete blood count, PT, PTT, and HbA1c will be obtained.
- 1.6.1.21** X-Ray of the study ulcer will be performed in cases of suspected osteomyelitis.
If the X-Ray is inconclusive regarding osteomyelitis, further investigation can be undertaken at the discretion of principal investigator. As stated below in the exclusion criteria, patients with underlying osteomyelitis will be excluded.
- 1.6.1.22** During the screening period the wounds will be treated weekly with standard of care treatment .
- 1.6.1.23** Investigator subjective wound pain assessment (appendix XX)
- 1.6.1.24** Medical staff wound related weekly labor assessment for the week prior to initiation of the screening (appendix XX) (optional per sponsor instruction)
- 1.6.1.25** Wound treatment cost assessment for the period prior to initiation of screening (at least weekly cost, preferably monthly cost, if

possible- cost since start of wound treatment)-)optional per sponsor instruction).

1.6.2 Treatment Phase Initial (Day 0):

- 1.6.1.1** Adverse event assessment.
- 1.6.1.2** Ulcer and blood related concomitant medication review.
- 1.6.1.3** Investigator subjective wound pain assessment
- 1.6.2.1** Photography before and after cleansing and debridement (if applicable)
- 1.6.2.2** Wound measurement by photography. Two measurements- before and after cleansing and debridement.
- 1.6.2.3** Wound depth measurement by accepted method. Unit of measurement is millimeters. Two measurements- before and after cleansing and debridement
- 1.6.2.4** Ulcer cleansing
- 1.6.2.5** Ulcer debridement as needed
- 1.6.2.6** Application Regimen: as per the investigators Brochure. Up to 3 RD1 dressings can be applied on each wound on each visit, according to wound size and investigator decision of subject health. The RD1 will be removed or applied only by the research staff.
- 1.6.2.7** Wound related staff labor assessment (optional per sponsor instruction)

1.6.3 Treatment Phase. (Weeks 1-16): The following treatments and assessments are performed during the treatment phase weeks 1-16. During the treatment phase there are 2 types of visits: **1. RD1 Change Assessment Visit** **2. RD1 Change Visit** (performed immediately after Change Assessment Visit).

1.6.3.1 RD1 change assessment visit procedures every 7 days (± 3 days):

- 1.6.3.1.1** RD1 change will be assessed by investigator
- 1.6.3.1.2** Wound/ blood related adverse event assessment
- 1.6.3.1.3** Assess offloading compliance when applicable.
- 1.6.3.1.4** Assess moisture control when applicable.
- 1.6.3.1.5** Ulcer and blood related concomitant medication review.
- 1.6.3.1.6** Photo the RD1 on the ulcer.
- 1.6.3.1.7** Assessment of the edges of the wound to assess infection.
- 1.6.3.1.8** Assessment of the adherence of the RD1 to the wound.

1.6.3.2 RD1 re-application visit procedures (occurs if investigator decides to change RD1, should occur immediately after RD1 change assessment visit):

- 1.6.3.2.1 Investigator subjective wound pain assessment pre RD1 removal
- 1.6.3.2.2 Removal of old RD1
- 1.6.3.2.3 Photography after RD1 removal, before cleansing and debridement.
- 1.6.3.2.4 Wound measurement by photography. Two measurements- before and after cleansing and debridement.
- 1.6.3.2.5 Wound depth measurement by accepted method. Unit of measurement is millimeters. Two measurements- before and after cleansing and debridement
- 1.6.3.2.6 Wound assessment.
- 1.6.3.2.7 Ulcer cleansing.
- 1.6.3.2.8 Ulcer debridement as needed.
- 1.6.3.2.9 Assess wound infection.
- 1.6.3.2.10 Application Regimen: as per the investigators Brochure. Up to 3 RD1 dressings can be applied on each wound on each visit, according to wound size and investigator decision of subject health. The RD1 will be removed or applied only by the research staff.
- 1.6.3.2.11 Assessment of wound closure
- 1.6.3.2.12 Wound related staff labor (optional per sponsor instruction)
- 1.6.3.2.13 RD1 clot residues sent to analysis

1.6.3.3 Wound healing confirmatory visit. Will be performed to assess durability of wound closure. Performed at the earlier of the 2 options: 1. before discharge from SNF. 2. Two weeks after complete healing. For wounds that have healed during the 16 weeks of active treatment.

- 1.6.3.3.1 Wound size measurement by photography.
- 1.6.3.3.2 Wound depth measurement by accepted method. Unit of measurement is millimeters
- 1.6.3.3.3 Investigator assessment of healing
- 1.6.3.3.4 Physical examination
- 1.6.3.3.5 Adverse event assessment.
- 1.6.3.3.6 Assess offloading compliance.
- 1.6.3.3.7 Concomitant medication review.
- 1.6.3.3.8 Laboratory: complete blood count, PT, PTT, and HbA1c
- 1.6.3.3.9 Offloading (for up to 2 weeks after wound healing, when applicable)
- 1.6.3.3.10 Investigator subjective wound pain assessment
- 1.6.3.3.11 Wound related staff labor during the whole RD1 treatment period (optional per sponsor instruction)
- 1.6.3.3.12 Wound treatment cost during the whole RD1 treatment period

1.6.3.4 End Of Study/ Early Termination Visit: At the end of week 16, for wounds that have not healed during the 16 weeks of active treatment or for early termination from the study, perform:

- 1.6.3.4.1** Investigator subjective wound pain assessment pre RD1 removal
- 1.6.3.4.2** Removal of old RD1
- 1.6.3.4.3** Wound size measurement by photography. Two measurements- before and after cleansing and debridement
- 1.6.3.4.4** Wound depth measurement by accepted method. Unit of measurement is millimeters. Two measurements- before and after cleansing and debridement.
- 1.6.3.4.5** Investigator assessment of healing
- 1.6.3.4.6** Physical examination.
- 1.6.3.4.7** Adverse event assessment.
- 1.6.3.4.8** Assess offloading compliance.
- 1.6.3.4.9** Ulcer and blood related concomitant medication review.
- 1.6.3.4.10** Laboratory: complete blood count, PT, PTT, and HbA1c
- 1.6.3.4.11** Wound related staff labor during the whole RD1 treatment period (optional per sponsor instruction)
- 1.6.3.4.12** Wound treatment cost during the whole RD1 treatment period (optional per sponsor instruction)

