1. OVERVIEW

1.1. Study Objectives

Primary Objective

The primary objective of this protocol is:

1. Efficacy- The performance of RD1 in terms of wound progress towards closure in wounds deemed suitable for treatment with RD1

Secondary Objectives:

Secondary objectives of the trial are:

1. Safety - Determine complication rates for all adverse events compromising serious adverse events, adverse events (AEs), and device-related adverse events (DRAEs); AEs include any lack of venous access events
2. Efficacy - Assess the incidence of complete wound closure at 16 weeks for wounds treated with RD1 (defined as skin re-epithelialization without drainage or dressing requirements).
3. Efficacy - Assess the wound Percent Area Reduction (PAR)
4. Efficacy- Assess the optimal duration between applications of RD1 per wound parameter
5. Efficacy- Assess the need of design and procedure improvements of the RD1 for specialized nursing facilities (SNF)
6. Sub Group Analysis – asses the safety and efficacy per wound etiology
7. Asses the cost of RD1 procedure in SNF compared to cost of treatment before RD1
8. Assess wound pain compared to wound pain during treatment before RD1
9. Assess medical staff wound related weekly labor of wound treatment before and during RD1.

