13.2.2. Secondary Endpoints

- Safety - Determine complication rates for all adverse events compromising serious adverse events, adverse events (AEs), and device-related adverse events (DRAEs); AEs include any lack of venous access events (ITT and Safety Population)
- Efficacy - Assess the incidence of complete wound closure at 16 weeks for wounds treated with RD1 (defined as skin re-epithelialization without drainage or dressing requirements) (ITT population).
- Efficacy - Assess the wound Percent Area Reduction (PAR) (ITT population)
- Efficacy- Assess the optimal duration between applications of RD1 per wound parameter (ITT population)
- Efficacy- Assess the need of design and procedure improvements of the RD1 for specialized nursing facilities (SNF) (ITT population)
- Sub Group Analysis – asses the safety and efficacy per wound etiology (subgroup of ITT population)
- Asses the cost of RD1 procedure in SNF compared to cost of treatment before RD1 (ITT population)
- Assess wound pain compared to wound pain during treatment before RD1 (ITT population)
- Assess medical staff wound related weekly labor of wound treatment before and during RD1. (ITT population)

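### During treatment the 0-10 pain score is scheduled only at visits where the investigator changes RD1 (plus the closing visit), so weeks with RD1 left in place have no score

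*Protocol*

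**What the plan says.** Secondary objective 8 (section 1.1, repeated as an endpoint in 13.2.2) is "Assess wound pain compared to wound pain during treatment before RD1".

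Section 1.6.3 divides treatment weeks into two visit types:

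- **Change assessment visit (1.6.3.1).** It is weekly: "RD1 change assessment visit procedures every 7 days", with a window of 3 days either way. Its first item is "RD1 change will be assessed by investigator". None of its eight items (1.6.3.1.1 to 1.6.3.1.8) is a pain score.
- **Re-application visit (1.6.3.2).** It follows at once, but only "occurs if investigator decides to change RD1". Its first item, 1.6.3.2.1, is "Investigator subjective wound pain assessment pre RD1 removal".

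The schedule of events (Appendix 7) agrees: the pain row is blank under the change assessment visit and marked under re-application. Appendix 15 defines the score as 0 to 10, rated by the investigator from observation before RD1 is taken off.

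Pain is also rated at screening, on day 0, at the healing confirmatory visit (1.6.3.3.10) and at the end-of-study or early-termination visit (1.6.3.4.1).

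The regimen is RD1 every 7 days with the same window, but sections 1.4 and 1.5 add that the "investigator can prolong the duration between treatments based on medical decision". Secondary objective 4 is to find the best interval between applications.

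**The concern.** At a single visit the same investigator decides whether to change RD1 and, only if so, rates the subject's pain. If the state of the wound or the subject's discomfort plays any part in that decision, the scores collected are not representative of the treatment weeks. The weeks left out are those in which RD1 stayed on.

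Prolonged intervals are foreseeable in this trial, because the protocol allows them without a stated limit and makes the interval itself an object of study. Subjects with longer intervals would contribute fewer scores, so coverage varies with the interval that objective 4 examines. A statistical analysis plan cannot repair this, since a score never taken cannot be recovered.

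At stake is one named secondary comparison, pain under RD1 against pain under the previous treatment. The primary endpoint is not affected.

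**Working it through.** **1. Where pain is scheduled, set side by side**

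| Visit | Depends on the decision to change RD1? | Pain score in 1.6 | Pain row in Appendix 7 |
|---|---|---|---|
| Screening and day 0 | No | Yes | Marked |
| Weekly change assessment (1.6.3.1) | No | None | Blank |
| Re-application (1.6.3.2) | **Yes** | Yes (1.6.3.2.1) | Marked |
| Healing confirmatory (1.6.3.3) | No, but after healing | Yes (1.6.3.3.10) | Marked |
| End of study or early termination (1.6.3.4) | No | Yes (1.6.3.4.1) | Marked |

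The visit lists and the schedule agree, and Appendix 15 ties the rating to removal. This is the design and not a slip in one list.

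**2. How many weeks carry a score**

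Inputs from the protocol: weekly visits, 16 weeks of treatment (day 112), and a closing visit at the end of week 16 for unhealed wounds. Assumptions: a constant change interval of d days and no missed visits. The protocol gives no distribution of intervals.

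Weeks with a score = (number of multiples of d from day 7 to day 105) + 1 for the week-16 visit.

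| Interval d | Change visits before week 16 | Plus week 16 | Weeks scored | Weeks without a score |
|---|---|---|---|---|
| 7 days | 15 | 1 | 16 of 16 | 0% |
| 14 days | 7 (days 14, 28, ..., 98) | 1 | 8 of 16 | 8/16 = 50% |
| 21 days | 5 (days 21, 42, ..., 105) | 1 | 6 of 16 | 10/16 = 62.5% |
| 28 days | 3 (days 28, 56, 84) | 1 | 4 of 16 | 12/16 = 75% |

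**3. What selection could do to the mean**

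This is an illustration only, and every input is assumed. Pain is 6 at 30% of weekly visits and 2 at 70%, so the mean over all weeks is 0.3 × 6 + 0.7 × 2 = 3.2.

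- RD1 changed at 90% of painful and 50% of other visits: recorded mean = (0.27 × 6 + 0.35 × 2) / (0.27 + 0.35) = 2.32 / 0.62 = 3.7.
- RD1 changed at 50% of painful and 90% of other visits: recorded mean = (0.15 × 6 + 0.63 × 2) / (0.15 + 0.63) = 2.16 / 0.78 = 2.8.

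The error can go either way, and the collected data would not show which. If the decision to change is unrelated to pain, the mean is not biased and the only loss is fewer scores.

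**4. With the fix**

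With a score at every change assessment visit, the same wound has 15 + 1 = 16 of 16 weekly scores whatever the interval.

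**The case against.** The strongest reply is that the stated regimen is weekly, and on that regimen nothing is missing. Gaps arise only when an interval is prolonged, and the protocol gives no frequency for that. This stands: the rows for 14, 21 and 28 days are hypothetical. It does not remove the point, because prolongation is expressly allowed and the interval is a study question.

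Second, rating pain just before removal is a consistent anchor, and asking for more scores may look like a taste for denser sampling. The anchor is consistent, but the objection here is to who decides when a score is taken, not to how many there are.

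Third, notable pain between changes would not pass unseen. Adverse events are assessed at every change assessment visit, marked pain on applying or removing the product is an example of a device-related event (7.2), and increased pain is one of the infection criteria (Appendix 11). That limits the clinical consequence, but none of these is the 0-10 score that objective 8 needs.

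A reader might also infer that staff labour suffers in the same way, since its Appendix 7 row has the same blank cell, and that weekly labour under RD1 is therefore overstated. The protocol does not support this. Objective 9 is to "Assess medical staff wound related weekly labor of wound treatment before and during RD1", and items 1.6.3.3.11 and 1.6.3.4.11 ask for labour over the entire course of RD1, which includes weeks without a change. That record is optional, but so is every other labour item in the visit lists. An overstatement would require averaging the re-application records alone, and the protocol states no such analysis.

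**Conclusion.** The point holds for pain. Between day 0 and the closing visit, no 0-10 score is scheduled in a week when RD1 is left in place, and the person who rates pain decides which weeks are scored. With constant intervals of 14 to 28 days and an unhealed wound, 50% to 75% of the 16 weeks would have no score; with 7-day changes, none would be missing.

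Two limits apply. The actual share is unknown, because the protocol does not say how often intervals are prolonged. The direction of any bias is also unknown, because nothing in the protocol links pain to the decision to change.

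It would be too strong to say that pain during treatment is scored at change visits and nowhere else: the end-of-study or early-termination score does not depend on that decision, though it is a single rating per subject. It would equally be too strong to say that the trial will overstate or understate pain. This is a worthwhile correction to one secondary endpoint, not a threat to the trial's main result.

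**What to change.** - Add the 0-10 pain score, taken with RD1 in place, to the change assessment list in 1.6.3.1, and mark the pain row in that column of Appendix 7. When a change follows at once, this score can serve as the pre-removal score.
- Reword the timing in Appendix 15 so that it covers a score with RD1 in place whether or not removal follows.
- For labour, no new collection is needed on this ground. Where labour is collected, base mean weekly labour under RD1 on the whole-period record and not on the re-application records alone.

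The cost is one extra investigator score at a weekly visit that already takes place. No treatment rule changes.

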4. STOPPING RULES

4.1. Individuals

4.1.1 Infection

An infection that cannot be controlled or interferes with treatment in such a way that a treatment failure is likely to occur.

If cellulitis or local wound infection occurs, the Investigator may interrupt treatment in order to address this adverse event. The Investigator will treat cellulitis or local wound infection in accordance with his clinical judgment. Systemic antibiotic therapy is permitted; however, topical antimicrobials are not permitted in combination with RD1. Investigator may interrupt treatment in order to apply topical antimicrobials and resume treatment later (in the time frame of 16 weeks only)

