4.1.3 Ulcer Deterioration

Ulcer deterioration, determined by physician discretion.

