6. MISSED VISITS

If a subject misses a visit, the site is to make every effort to have the subject return as soon as possible to make-up the visit. Once the subject is seen, he/she is to return to his/her original visit schedule.

Patients who miss more than 2 two consecutive visits during the treatment phase will be withdrawn.

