8. PREMATURE WITHDRAWAL OF SUBJECTS

Subjects have the right to withdraw from the study at any time for any reason. The investigator also has the right to withdraw a subject from the study, if he/she seems it to be in the subject's best interest. It is recognized that an excessive rate of withdrawals may render the study uninterrupted and, therefore, it is desirable to avoid unnecessary withdrawals.

While lack of venous access is not anticipated as a major problem, a subject will be withdrawn from the trial if the investigator cannot find venous access during the treatment study visits (Visits 1-16).

Noncompliance with study treatment/ offloading in a manner that interrupt treatment and delay healing, according to principal investigator judgment

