Neuropathic Assessment- foot ulcers only

Sensory neuropathy will be quantified using the Semmes-Weinstein test to evaluate the 10 locations shown in Figure 1. For this trial, the 10 g 5.07 gauge monofilament will be used. The number of sites where the subject does not perceive sensation will be recorded in the CRF.

Figure 1. Semmes-Weinstein 10 Point Sensory Neuropathy Screen

APPENDIX 11
INFECTION ASSESSMENT

Infection of the index wound will be determined by the physician, taking into account the following parameters:

1. Increased surface area, depth or grade.
2. Increased periwound margin temperature by more than 3°F difference between 2 mirror image sites;
3. New areas of breakdown or satellite lesions
4. Presence of swelling or reddened skin in periwound area
5. Increased wound drainage
6. Unpleasant, sweet, or sickening odor present.
7. Excessive bleeding on a wound
8. Increased pain of the wound

In the case the wound has exposed bone or can be probed to the bone, the patient will be withdrawn from the study.

APPENDIX 12

MOISTURE CONTROL ASSESSMENT

Assessment of moisture control will be based upon determining whether there is maceration at the skin edge. If there is maceration, clinicians will be instructed to examine whether the secondary absorbent dressing is appropriate, or whether excessive exudation is taking place. The clinician may also elicit discussion with the patient regarding care of the wound.

APPENDIX 13
OFFLOADING DEVICE INSTRUCTIONS

Offloading will be assessed at each visit and determined whether it is adequate, and whether patient compliance is satisfactory. Because there is little evidence to suggest that one type of offloading is superior to another, if a pressure-relieving surface is being utilized for a truncal ulcer (such as an appropriate overlay or alternating/low-air-loss mattresses for full-thickness ulcers), appropriate footwear for a heel ulcer (active offloading walker (boot and/or shoe)), or suitable pressure relief for any other ulcer location, then offloading will be regarded as adequate. If this is not the case, the patient will be further educated.

For subjects who do achieve complete closure during the treatment phase, use of the offloading device is recommended for at least 2 weeks.

APPENDIX 14
STANDARD CARE

The study center will provide the study ulcer with standard care during screening period, per physician discretion

APPENDIX 15
INVESTIGATOR SUBJECTIVE ULCER PAIN ASSESSMENT

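### Subjects who permanently stop RD1 or are withdrawn have no wound assessment after the early-termination visit, so their week-16 area and closure are not observed

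*Protocol*

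**What the plan says.** **Endpoint.** Protocol 13.2.2 sets as a secondary endpoint: "Assess the incidence of complete wound closure at 16 weeks for wounds treated with RD1". Percent area reduction is another secondary endpoint. The primary endpoint (13.2.1) is wound progress towards closure.

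**Last visit.** The end-of-study/early-termination visit in 1.6.3.4 opens with the end of week 16 and then applies "for wounds that have not healed during the 16 weeks of active treatment or for early termination from the study". It records area, depth, the investigator's assessment of healing and adverse events, and it includes removal of the RD1. Appendix 7 has five visit columns. None is for a subject who is off RD1 but still under observation.

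**Exit rules.**
- Section 8: "a subject will be withdrawn from the trial if the investigator cannot find venous access during the treatment study visits".
- Section 6: "Patients who miss more than 2 two consecutive visits during the treatment phase will be withdrawn".
- Appendix 11, for exposed or probed bone: "the patient will be withdrawn from the study".
- Section 4.1 lists individual stopping reasons, among them "Ulcer deterioration, determined by physician discretion", uncontrolled infection, health deterioration and substantial necrotic tissue. It does not say whether a stopped subject stays in the study.
- Appendix 5 has a central reviewer look at wounds enlarged by 50% or more, or raised in grade, to confirm whether the subject should be withdrawn.

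**Resumption.** Section 4.1.1: "Investigator may interrupt treatment in order to apply topical antimicrobials and resume treatment later", within the 16 weeks. Section 7.4 allows resumption after return from another facility in some cases, with sponsor approval.

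**Consequence for the analysis.** Section 1.2: "if any patients are lost to follow-up or withdrawn, enrollment will increase to compensate for loss of these subjects". Section 9 keeps only completers in the secondary-objective analyses and uses LOCF for missing wound area. Section 13.1.2 defines the set called ITT as completers, and the primary endpoint uses that set.

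**The concern.** The visit schedule does not distinguish a subject who has stopped RD1 from one who has left the study. Once a stop is permanent, nothing requires anyone to look at the wound at week 16, the time at which closure is defined. This is a matter of data collection, so an SAP cannot repair it: redefining the analysis set does not create a value that was never recorded, and LOCF only carries forward the measurement taken at exit.

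The loss is unlikely to be random. Infection, ulcer deterioration, health deterioration, necrotic tissue and marked enlargement of the wound all go with poor healing, and in Appendix 5 possible withdrawal depends directly on measured wound area or grade. Replacing such subjects and analysing completers selects the wounds that did better. In a single-arm study no control group shares that selection.

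**Working it through.** **Step 1. Tracing the routes through the visit schedule.**

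| Route | Wound assessment at week 16? |
|---|---|
| Stays on RD1, wound open | Yes, 1.6.3.4 |
| Heals within 16 weeks | Closure recorded, then the confirmatory visit (1.6.3.3) |
| RD1 interrupted and resumed (4.1.1, 7.4) | Yes, can still reach the week-16 visit |
| RD1 left in place longer by investigator decision | Yes; change-assessment visits run every 7 days whether or not RD1 is changed |
| Permanent stop under 4.1 | None scheduled; status in the study not stated |
| Withdrawn under 6, 8 or Appendix 11 | None scheduled after early termination |

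The gap lies in the last two rows only.

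**Step 2. Can the planned sample size be used to judge the effect?** No. Section 13.1.3 sets 60 completers without a closure rate, reference rate, precision target or drop-out rate. There is nothing to reproduce, and the point does not depend on the figure being right.

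**Step 3. Size of the effect under assumptions.**

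Inputs:
- 60 completers (1.2, 13.1.3).
- Completer closure p = 60%, i.e. 36 of 60. Assumed.
- Share stopped d. Assumed at 10%, 20% and 25%. The 25% happens to equal the study-level stopping threshold for drop-out from venipuncture problems (item 4.2.3), but that is a threshold and not an expected rate.

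Formulas: treated N = 60/(1 − d), rounded up; unmeasured s = N − 60; lower bound = 36/N (no unmeasured wound closed); upper bound = (36 + s)/N (all closed).

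| d | N | s | Lower | Upper | Stopped subjects close at half the completer rate |
|---|---|---|---|---|---|
| 10% | 67 | 7 | 36/67 = 53.7% | 43/67 = 64.2% | 56.9% |
| 20% | 75 | 15 | 36/75 = 48.0% | 51/75 = 68.0% | (36 + 4.5)/75 = 54.0% |
| 25% | 80 | 20 | 36/80 = 45.0% | 56/80 = 70.0% | (36 + 6)/80 = 52.5% |

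**Step 4. Comparison with sampling error.** The 95% half-width at n = 60 is 1.96 × √(0.6 × 0.4/60) = 12.4 points. The exact interval for 36/60 is 46.5% to 72.4%, about 13 points either side. The possible downward shift from 60% is 60 − 48 = 12 points at d = 20% and 60 − 45 = 15 points at d = 25%. At those shares the uncertainty from unobserved outcomes is about as large as sampling error, or slightly larger, and more subjects enrolled under the same rules would not reduce it.

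**The case against.** **The outcome may already be known.** The endpoint concerns wounds treated with RD1. If a subject stops with an open wound and that counts as not closed, the early-termination visit supplies the answer, and closure reached later under other care would say nothing about RD1. This stands in part. It is a legitimate way to count closure, and the fix includes it. But the protocol does not count these subjects as failures; it replaces and excludes them. Nor does that rule supply week-16 area for percent area reduction or for the primary endpoint.

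**Week 16 may govern both clauses.** In 1.6.3.4 the opening reference to the end of week 16 could be read as timing the early-termination assessments too. The visit title and the RD1-removal step point to a visit at termination. The ambiguity is real and needs correcting in either case.

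**Missed visits are not device failures.** Section 6 concerns non-attendance and already asks sites to bring the subject back. Some of these subjects will not be obtainable at week 16. That stands, and it limits what the fix can recover.

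**Stronger readings that a reader might infer, and that the protocol does not support:**
- *Every stop of RD1 ends observation.* Sections 4.1.1 and 7.4 allow resumption, and 4.1 does not itself equate stopping with leaving.
- *Most stopped subjects are still resident in the SNF.* No share is given, and hospitalization, referral and missed visits point the other way. The point needs only that some could be seen.
- *Half of the subjects could be lost, taking 120 from section 1.3 against 60 completers.* Section 1.3 gives an enrolment ceiling in two phases and nowhere implies 50% drop-out.
- *An entry criterion on availability to week 16 is missing.* Such a criterion is a trade-off, since it could exclude short-stay residents. A subject discharged unhealed can still have the wound recorded at the early-termination visit.

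**Conclusion.** The point holds for permanent stops and withdrawals. For them the protocol schedules no wound assessment after early termination, so week-16 area and closure are not observed even where they could be. Because exits are tied to poor healing and efficacy is restricted to completers, the completer closure rate is probably too high.

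The size cannot be fixed from the protocol. With 60 completers and an assumed 60% closure, closure among all treated spans 20 points (48% to 68%) if 75 are treated and 25 points (45% to 70%) if 80 are treated. The upper ends are extreme: they require every stopped wound to close, including those stopped for deterioration or necrosis. The realistic direction is downward. If few subjects stop, the effect is small: at 10% the lower bound is 53.7%.

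This is a change the sponsor should make. It does not invalidate the study, and it rests on no judgement about the clinical stopping rules.

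**What to change.** 1. In 1.6.3.4 and sections 4.1, 6 and 8, separate two statuses: RD1 stopped, and withdrawn from the study. Bring Appendix 11 and the Appendix 7 schedule into line. State in 4.1 that a stopped subject remains in the study unless consent is withdrawn, and in 1.6.3.4 say when the early-termination assessments are done.
2. Where consent stands and the subject can be reached, perform the wound assessments already defined for week 16 (photograph, area, depth, closure, adverse events) and flag them as off RD1.
3. Amend section 9 and 13.1.2 so that all treated subjects enter the efficacy analysis. Without this step the new values would be collected and then excluded.
4. Report closure also with every subject who stopped RD1 with an open wound counted as not closed, so that closure under later care is not credited to RD1.

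**Cost.** Protocol wording and one extra assessment per stopped subject, some of which will not be obtainable. Off-RD1 values have to be reported separately, and the closure rate may come out less favourable. The target of 60 completers need not change for this purpose, and no change to when RD1 is stopped is proposed.
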